The overall purpose of this protocol is to assess the biomechanical and neurophysiologic effects of rehabilitative strategies and protocols that are commonly used during physical therapy treatment of gait disorders post-stroke. As part of this protocol, 45 able-bodied individuals and 55 individuals with chronic stroke will be assigned to either Cohort 1 or Cohort 2, and will participate in 1-18 gait training sessions. If interested, study participants can also complete both study cohorts sequentially (with at least 3-weeks duration between switching from one cohort to the second). Evaluations for obtaining outcome measures will comprise clinical testing, muscle evaluations, gait analysis, and assessment of spinal and corticospinal excitability. Within Cohort 1 (stroke and able-bodied), 25 subjects will receive identical treatment throughout the training sessions (i.e. FastFES training). Within Cohort 2, 25 subjects will receive different rehabilitation strategies individually or in combination during each training session (e.g., treadmill walking, functional electrical stimulation, bio-feedback or verbal feedback about targeted walking parameters, split-belt walking, etc.). During gait training, Cohort 1 subjects will typically participate in a minimum of 2 and a maximum of 3 sessions per week. Subjects in Cohort 2 can participate in 1 to 18 gait training sessions but the frequency of the gait sessions can be varied according to the subject's and laboratory schedule (i.e. variable durations between consecutive sessions).

Aims

The aims of this protocol are to:

- 1) Study the changes in gait biomechanics, corticospinal excitability, and walking function during 18 sessions of gait retraining (Cohort 1).
- 2) Systematically determine the effect of parameters such as walking speed (slow, fast, variable, split-belt walking), functional electrical stimulation parameters (short-term changes induced by fast versus FastFES, stimulation intensity, number of muscles stimulated), and bio-

[figure not shown]
feedback on within-session changes in gait biomechanics, walking function, and corticospinal excitability (Cohort 2).

Hypotheses of the study

- By utilizing data collected on cohort 1 of subjects who undergo 18 sessions of FastFES gait retraining, the following hypothesis will be tested:

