 - H1.* Eighteen sessions (6-8 weeks) of gait training comprising fast treadmill walking and functional electrical stimulation (FastFES) will result in Improvements in gait biomechanics, corticospinal excitability, and walking function.
 - H2.* Improvements in gait biomechanics will precede the improvements in corticospinal excitability and walking function.
 - H3.* Improvements in walking function will be correlated to improvements in corticospinal excitability.
- By utilizing data collected on cohort 2 of subjects who receive different rehabilitation strategies during each training session, we will analyze short-term changes induced by 1-3 sessions of gait retraining to test the following hypothesis:
 - H4.* The magnitude of improvements in gait biomechanics and corticospinal excitability will be greater for gait training sessions that comprise:
 - walking at a faster versus slower speed
 - walking with versus without FES, i.e. Fast versus FastFES
 - walking with FES delivered to two versus one muscle during gait
 - walking with 2 belts going at different speeds or directions versus regular treadmill walking
 - walking with versus without visual bio-feedback or other feedback (e.g. verbal, tactile) about targeted parameters during gait
 - greater dosages (# of walking steps per session) of walking practice
 - combination of 2 strategies versus a single rehabilitation strategy

5. Study design and methods

Research Procedures

Flowchart showing the overview of study procedures.

The overall goal of this protocol is to provide novel insights into the biomechanical and neural mechanisms underlying gait rehabilitation. To achieve this goal, a series of experiments will be performed on young able-bodied individuals as well as stroke survivors. The protocols to be tested and procedures to be used are described in detail here. For all the procedures and sessions described below, all testing procedures will be explained to the subject at the beginning of each testing session. Also,

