during these testing procedures, rest breaks will be provided to the subjects as needed and as requested by the subject. Please see the adjoining flowchart for a summary of the procedures that subjects in each study cohort will undergo. Subjects will not be randomized to the 2 cohorts. Assignment to the cohorts will be based on the lab/personnel and subject schedules. A subject can participate in the 2 cohorts sequentially. Also, participants in Cohort 2, when testing hypotheses comprising a repeated-measures comparison of different gait training strategies (e.g. Hypothesis 4a evaluating effect of walking speed; Hypothesis 4b comparing FastFES versus Fast), participants may cross-over between strategies within or across gait sessions.

1) Medical Clearance:

If a subject shows interest in participation in cohort 2 of the study (18 training sessions), before participation, we will obtain written medical clearance from the subject's physician (See attached Medical Clearance form). In addition, the subject will undergo clinical assessment to confirm that they are eligible for study participation.

2) Procedures for Clinical Assessment of Walking Function and Muscle Strength:

All subjects will review and sign consent forms before clinical testing. Clinical Testing will be performed by a licensed physical therapist. Clinical testing may comprise: (1) measurement of subjects' over ground self-selected (SS) walking speed (6-meter walk test); (2) over ground walking endurance measured by the distance ambulated during the 6-minute walk test; (3) assessment of gait and dynamic balance (measured using the functional gait assessment, 4-square step test, and the Berg balance score); (4) lower extremity portion of the Fugl-Meyer score⁷⁰; (5) step activity monitoring; (6) lower extremity proprioception (in which each limb segment will be flexed or extended approximately 10 degrees and the subject will be asked to identify whether the limb is moving and in what

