For gait training, as part of Cohort 1, the subject will receive the same type of walking training (fast treadmill walking with electrical stimulation) for all 18 sessions and participate in 2-3 training sessions per week over the course of 6-weeks. For cohort 1, the gait training sessions may comprise up to six 6-minute bouts of walking with rest breaks between bouts (total 30-minutes of walking). The last training bout (bout 6) may comprise 6-minutes of over ground walking (Fig. 1), during which subjects will be asked to walk as fast as they can. For safety, a physical therapist will walk with and guard the subject during over ground walking. For cohort 1, outcome measures may be obtained before, after, and intermittently throughout the 6-weeks of training (e.g. clinical testing, muscle strength testing, and assessment of corticospinal and spinal excitability).

Subjects in Cohort 2 will receive different types of walking training (e.g. treadmill walking at slow or fast speed, training with (FastFES) or without stimulation (Fast), training with or without feedback, etc.) for each of the training sessions, and will complete 1-3 training session per week with a variable delay (1-day to several weeks) between consecutive sessions. For cohort 2, outcome measures may be obtained before, after, and intermittently during each of the training sessions (e.g. clinical testing, muscle strength testing, and assessment of corticospinal and spinal excitability). For Cohort 2, when the subject receives different types of training during each of the 18 sessions, the training may comprise a total of 10 to 40-minutes of different types of walking. Depending on the gait training strategy being tested during the session, the session may comprise one or more of the following:

- Treadmill walking at a range of walking speeds (ranging from slower than comfortable self-selected speed to the subject's fast walking speed)
- Electrical stimulation applied to the ankle muscles at appropriate phases of the gait cycle during gait training
- Walking with both treadmill belts running at different speeds or directions
- Greater versus smaller dose of walking practice (three versus six 6-minute bouts)
- Bio-feedback, visual cues, or verbal / tactile cues regarding specific parameters of gait such as push-off forces, knee flexion angle during swing phase, etc.

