Hypotheses testing will be done with a p-value set at 0.05. The outcome variables used for analyses will include peak knee and ankle flexion during walking, propulsive forces during walking, walking speed and endurance, peak and duration of EMG activation during walking, and TMS-derived measures of corticospinal excitability (peak EMG in response to TMS, motor threshold intensity, slope and peak of the TMS-recruitment curve). To test *H1*, for each of the variables, one-way repeated measures ANOVA will be performed to check for differences in the variable after versus before 18 sessions of training. To test *H2*, we will plot the dependent variable versus time (test session number). Using these plots, the time to plateau and the time when the variable first shows a positive within-session change (threshold time) will be determined. One way repeated measures ANOVA will be used to compare the time to plateau and threshold time among 3 variables – peak propulsion, peak TMS muscle response, and over ground walking speed. To test *H3*, a Pearson's correlation will be performed between the change in peak propulsion after training versus change in peak TMS muscle response after training. For the hypothesis involving within-session changes (*H4*), repeated measures ANOVA will be performed to compare the within-session percentage change for each variable between different rehabilitation strategies.

Power Analysis: The current protocol has been powered using the primary outcome measure of paretic propulsive force generation. Based on means and standard deviations from our existing pilot data, for each aim, a sample of 24 subjects will provide 80% power to detect a 4.2% difference in propulsive force between sessions with standard deviation of 6% at a two-sided alpha level of 0.05. After completion, the data from this study will be used to conduct systematic power analysis for other outcome variables, which will be utilized to design a larger-scale future study.

8. Adverse event reporting

We will notify the IRB of any adverse events that occur during the protocol.

10. Device information

Equipment for Motion Analysis and Gait Retraining: A 7-camera system will be used to collect motion analysis data (Vicon, Oxford, UK). Ground reaction forces during treadmill walking will be collected using a treadmill instrumented with two 6-component force platforms under each

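### H4 compares training strategies within participants, but no readable text sets the order of strategies and the planned ANOVA names no period term

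*Combined protocol and SAP*

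**What the plan says.** Section 7 gives the H4 test in one sentence: "repeated measures ANOVA will be performed to compare the within-session percentage change for each variable between different rehabilitation strategies". Strategy is the only factor mentioned.

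Under Research Procedures, section 5 says of Cohort 2 that "participants may cross-over between strategies within or across gait sessions". Item 4 of section 5 (Procedures for Gait Training Sessions) describes H4b, FastFES against Fast, as a repeated-measures comparison. It says that these data, together with those of Cohort 1, will help to plan and size a larger trial.

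On order, the readable text is silent. The statement that subjects are not randomised concerns the two cohorts. The three-week gap in section 4 is also between cohorts. The only random order described is that of TMS pulse intensities (section 5, item 8). Research Procedures also says "Please see the adjoining flowchart for a summary of the procedures", but that flowchart is not shown in the text available.

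On measurement, the pre-test and post-test of each session are optional in item 4, and "For cohort 2, outcome measures may be obtained before, after, and intermittently during each of the training sessions".

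On the number of sessions, section 4 says "Subjects in Cohort 2 can participate in 1 to 18 gait training sessions", but for H4 it says "we will analyze short-term changes induced by 1-3 sessions of gait retraining to test the following hypothesis".

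**The concern.** In a within-participant comparison, anything that changes from one session to the next is mixed with strategy unless the order is balanced or modelled. The H4 outcome protects against part of this: change from the same session's pre-test removes drift or carry-over in level. It does not remove a trend in the gain itself, for example through practice, fatigue or diminishing returns.

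The plan allows for such a trend. For H2 it says that "the time to plateau and the time when the variable first shows a positive within-session change (threshold time) will be determined". The threshold time presupposes that the within-session change can differ between sessions. That analysis belongs to Cohort 1, so it shows that the plan regards a trend as possible. It does not show that one exists in Cohort 2.

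If one strategy tends to come later, its estimated advantage includes part of the trend. The H4b estimate would carry that bias into the planning of the larger trial. If every participant has the same order, no later analysis can separate the two.

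Where strategies are crossed within one session, tests only at its start and end cannot attribute the change to either strategy.

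**Working it through.** **Inputs from the plan.** Section 7, Power Analysis: "a sample of 24 subjects will provide 80% power to detect a 4.2% difference in propulsive force between sessions with standard deviation of 6" (in percent), at two-sided alpha 0.05. The plan does not say whether this is the SD of the paired difference.

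**The plan's own figure.** With SD 6% for the paired difference, the standardised effect is 4.2/6 = 0.70, and a paired t-test with n = 24 has 90.7% power, not 80%. Power of 80% at n = 24 needs a standardised effect of 0.597, that is an SD of 4.2/0.597 = 7.03%. Both SDs are carried through below.

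**Assumptions.** The documents give neither the trend in gain nor the order split. Trends of 1, 2.1 and 4.2 points are assumed, the largest being equal to the whole target effect.

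**Model.** For a two-strategy contrast, the paired difference is effect + trend + error in one order and effect − trend + error in the other. The planned two-level repeated measures ANOVA is then a one-sample t-test on these differences. The period-adjusted estimate is the mean of the two order-group means, with pooled SD and 22 degrees of freedom.

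**Bias without a period term.** Bias = trend × (n1 − n2)/n. At 18:6 the factor is (18 − 6)/24 = 0.5, so a 2.1-point trend gives 1.05 points. With one order for all the factor is 1.

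**One order for all.** The noncentrality is trend × √24 / SD. At SD 6% it is 0.82, 1.71 and 3.43, giving the last row below.

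**False-positive rate without a period term** (nominal 5%; simulation except the last row; trends of 1 / 2.1 / 4.2 points):

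| Order split | SD 6% | SD 7.03% |
|---|---|---|
| 14:10 | 4.9 / 4.6 / 3.5% | not needed |
| 16:8 | 5.5 / 6.9 / 10.6% | 5.3 / 6.4 / 9.4% |
| 18:6 | 6.5 / 11 / 26% | 6.2 / 9.5 / 21% |
| One order for all | 12 / 38 / 91% | 10 / 29 / 80% |

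**With a period term** the rate is 4.9% to 5.1% at every split where both orders occur.

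**Order left to chance.** If each participant's order is equally likely to fall either way, the unadjusted rate is 5.0% for all three trends at SD 6% and 5.0% to 5.1% at SD 7.03%. A split of 18:6 or worse then has probability 2.3%, and 14:10 or better has 69%.

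**Power for a true 4.2-point effect, SD 6%.**
- With the period term: 90.6% (12:12), 87% (16:8), 81% (18:6). At SD 7.03%: 80%, 75%, 68%.
- Without the term, at 18:6 and with the trend running against the better strategy: 82%, 66% and 26% for the three trends.
- Without the term, at 12:12 and with a 4.2-point trend: power falls from 91% to about 80%.

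**The case against.** The strongest reply is that the harm needs a systematic order, and nothing in the documents shows one. This stands: haphazard ordering leaves the error rate at 5%, and a mild imbalance does no damage. A reader might infer that the H4 test is invalid as written, and that goes too far. What remains is that a study run exactly to this text could give everyone Fast before FastFES.

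The missing flowchart may contain an order rule. A reader might infer that the plan has none, but only the readable text can be judged. Even with such a rule, section 7 would still name no period term.

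The H4 sentence does not exclude a period factor: H1 and H2 specify a one-way analysis and H4 does not. That is fair, but a plan should state the factor it intends to use.

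A reader might also draw on the H2 plateau, or on the allowance of up to 18 sessions, to argue for a strong trend. Neither helps. The plateau is read from a plot of the variable itself, so it concerns level, and H4 is limited to changes over 1 to 3 sessions.

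Finally, a reader might infer that the larger trial would be too small by a definite fraction. The documents do not support that. At 18:6 with a 2.1-point trend the estimate could be 4.2 + 1.05 = 5.25 or 4.2 − 1.05 = 3.15, so the error could go either way. The SD of the differences would also rise, to √(36 + 2.1² × 0.75) = 6.27. And nothing says that the H4b mean difference will be the target effect of that trial.

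**Conclusion.** The concern holds as a gap in design and analysis whose size is conditional. The readable plan permits a common or lopsided order of strategies and names no term that would adjust for it. With n = 24 and an SD of the difference of 6%, the consequence ranges from nothing (chance order, or a split near balance) through 6.5%, 11% and 26% false positives at a fixed 18:6 split to 12%, 38% and 91% with one order for all. The lower rates at SD 7.03% do not change the conclusion. These figures rest on assumed trends and splits and on a two-strategy, two-period contrast. The single-order case matters most, because it cannot be repaired after the data are collected. The change should be made. Confidence is medium, because the flowchart cannot be seen and the trend is unknown.

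**What to change.** For each two-strategy H4 contrast:

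- Randomise or counterbalance strategy order per participant, and record the order used. If the flowchart already sets an order, state it in section 5.
- Require the pre-test and post-test, for the outcome being compared, in every session used for H4. Where strategies are crossed within a session, repeat them around each block.
- Keep the within-session change as the outcome, and state in section 7 that the H4 model includes strategy, period as a categorical factor, and a participant effect.
- State as a limitation that balancing does not remove carry-over in the gain that differs between strategies. At 12:12 with the period term and SD 6%, such carry-over of 1, 2.1 or 4.2 points would still give false-positive rates of 6.8%, 13% and 38%.

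The cost is an order list, a few lines of text, some extra 30-second walking tests (and extra excitability tests where those outcomes are compared), and less freedom in scheduling. The period term uses one degree of freedom in a two-period contrast, and more where there are more periods. With balanced order and no trend, power is about 90.6% with the term against 90.7% without it. At 18:6 with no trend it is 81% against 91%, so balance belongs in the design and should not be left to the model.

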Over 7.7 million people are living with the effects of a stroke and about 700,000 experience a stroke or a recurrence of stroke each year¹. Stroke is the leading cause of adult disability contributing to limitations in activities of daily living¹. More than 50% of stroke survivors have walking dysfunctions and receive gait rehabilitation². Even after rehabilitation, residual gait deficits are prevalent in stroke survivors^{2, 3}. Because gait dysfunction limits community mobility, most stroke survivors perceive improvement in their walking as a critical goal of rehabilitation^{4, 5}. There is consensus in the literature that similar to acute stroke patients, chronic stroke patients can benefit from rehabilitation⁶⁻¹³. Thus, there has recently been renewed interest in the rehabilitation research literature toward the development and improvement of gait retraining interventions^{9, 12-29}.

Post-Stroke Gait Dysfunctions

Normal walking is characterized by smooth progression of steps and symmetry between limbs³⁰. However, stroke results in weakness and inappropriate timing and gradation of contractions in muscles of the extremity affected by the stroke³¹⁻³⁴. Post- gait deficits affect all phases of the gait cycle and all lower extremity joints^{32, 34}. Common swing phase post-stroke gait deficits include reduced flexion at hip, knee, and/or ankle joints^{31, 32, 34, 35}. During the stance phase, decreased contribution of the paretic leg to forward propulsion during paretic terminal stance is a critical post-stroke gait deficit shown to be correlated with hemiparetic severity, walking speed, and gait asymmetry^{36, 37}. These gait deficits can lead to falls, increased energy cost of gait, and decreased endurance^{5, 33, 34, 38}. Also, a slowed self-selected walking speed is one of the hallmarks of post-stroke gait, and greatly limits community participation in individuals post-stroke³⁹.

One goal of recent rehabilitation research has been to maximize the efficacy of post-stroke gait rehabilitation by developing new treatments and improving existing interventions^{12, 16, 17, 40-42}. Recently, treadmill training has emerged as an intervention that can improve walking

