FastFES is a novel gait training intervention that combines the beneficial effects of 2 independent interventions: Fast treadmill walking and FES. The FastFES intervention incorporates principles of physiology^{57, 58}, biomechanics^{59, 60}, motor control and learning, and predictions of forward-dynamic gait simulations⁶¹⁻⁶³ to improve post-stroke gait. *The FastFES gait treatment serves as an excellent paradigm for understanding the mechanisms underlying post-stroke gait rehabilitation because:* (1) It employs principles of motor learning (high intensity of task-specific practice, inclusion of overground walking practice, alternating walking practice with and without FES) to maximize therapeutic benefits. (2) It utilizes a scientific hypothesis-based approach to target specific post-stroke gait deficits, i.e., slowed walking speed, decreased forward propulsion, decreased knee and ankle flexion during swing. (3) It capitalizes on the use of FES as a motor learning tool to facilitate practice and learning of the proper timing and intensity of muscle activations during gait^{15, 20, 21, 38, 47, 48, 64}. (4) While a typical gait rehabilitation treatment session provides practice of ~357 steps, a FastFES session may provide practice of as many as 2000 steps during one training session⁶⁵. *Data collected on Cohort 1 of this proposed project will examine the mechanisms underlying gait rehabilitation by collecting concurrent data on gait biomechanics, corticomotor excitability, and walking function during a series of FastFES gait training sessions. Data collected on Cohort 2 will enable us to evaluate the within- and across-session changes induced by different types of gait training strategies including FastFES or fast walking without FES. The 2 cohorts will provide critical information that will form the foundation for future studies.*

Need for understanding the time course and mechanisms of gait rehabilitation

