Surface electrical stimulation electrodes will be attached to the ankle dorsiflexor (2"X2", TENS, CO) and plantarflexor muscles (3"X5", VersaStim, ConMed Corp, NY). For the dorsiflexors, the cathode will be placed over the motor point of the tibialis anterior and the anode over the distal portion of the muscle belly of the tibialis anterior. For the plantarflexors, the cathode will be placed over the proximal portion and the anode over the distal portion of the gastrocnemius muscle belly. Next, stimulation intensity to be used during walking will be determined for each muscle. For ankle dorsiflexor muscles, intensity will be set to generate ankle dorsiflexion to a neutral ankle position when the subjects are seated with their leg suspended. For the ankle plantarflexor muscles, the intensity will be set to achieve lifting of the paretic heel off the ground, with the subject in a standing position⁶⁰. Maximal intensity will also be set based on subject tolerance.

An electrical stimulator will be used to deliver stimulation during walking (Grass S8800 stimulator with SIU8TB stimulus isolation unit; UDel stimulator). A customized, real-time system ^{59, 60, 75} (CompactRIO, National Instruments, TX) will be used to control the stimulator and deliver stimulation during appropriate phases of the gait cycle. Stimulation will be delivered to the ankle dorsiflexors when the subject's foot is in the air (swing phase). Stimulation will be delivered to the ankle plantarflexors during the terminal stance phase of gait. 30-Hz variable frequency stimulation trains ⁵⁸ will be delivered during gait.

7) Procedures for Assessment of Spinal Excitability:

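### H4 is tested on percentage change for every variable, including knee and ankle angles, which have no true zero; joint angles should be analysed in degrees

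*Combined protocol and SAP*

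**What the plan says.** Section 7 (Statistical analysis) sets one rule for H4: "repeated measures ANOVA will be performed to compare the within-session percentage change for each variable between different rehabilitation strategies". The variables are named earlier in the same section: "The outcome variables used for analyses will include peak knee and ankle flexion during walking, propulsive forces during walking", followed by speed, endurance, EMG and TMS measures. The section gives no formula or denominator for the percentage, no zero or sign convention for the angles, and no rule for pre-test values at or below zero.

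Three other places bear on the ankle angle:

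- Section 3, under Post-Stroke Gait Dysfunctions: "Common swing phase post-stroke gait deficits include reduced flexion at hip, knee, and/or ankle joints".
- Section 3, under FastFES, lists the deficits that the intervention targets: "slowed walking speed, decreased forward propulsion, decreased knee and ankle flexion during swing".
- Section 5, item 6 (Functional Electrical Stimulation) has the only mention of a neutral ankle. For the dorsiflexors, "intensity will be set to generate ankle dorsiflexion to a neutral ankle position when the subjects are seated with their leg suspended".

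No section reports a baseline joint angle in degrees.

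**The concern.** A percentage change is interpretable only if zero means none of the quantity and pre-test values lie well away from zero. Speed, distance and force have such a zero. An angle does not: its zero is a convention, and moving it changes every percentage while the movement itself stays the same. Because Section 7 does not state the zero, the H4 test variable for joint angles is not fully defined.

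The ankle is the sharper case. More ankle flexion in swing is the intended improvement. If the angle is measured from neutral, participants with little dorsiflexion will have pre-test values near zero, where a small gain becomes a very large percentage. If the denominator is also signed and the peak is taken in swing, a participant whose pre-test peak is below neutral has a true improvement scored as a worsening.

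H4 asks which strategy gives the greater improvement. It is the hypothesis for Aim 2, and the comparison of FastFES with fast walking is meant to inform a larger trial. A ranking on ankle flexion that is lost or reversed by the scale would carry forward.

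**Working it through.** **1. The plan's own figure.** The only sample-size figure in Section 7 is for paretic propulsive force: 24 subjects, 80% power, difference 4.2%, SD 6%, two-sided alpha 0.05. Taking 6% as the SD of the paired difference, the standardised effect is 4.2/6 = 0.70. A paired t-test then needs 19 subjects for 80% power, and 24 subjects give 90.7%. The stated 80% is therefore not reproduced from these inputs alone, but the discrepancy is on the cautious side and concerns another outcome. Only n = 24 is carried forward.

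**2. Dependence on the reference.** Give every participant the same gain of 3 degrees. Percentage change = 100 × (post − pre)/pre = 300/pre. If the same angle is expressed with its zero moved by 90 degrees, it is 300/(90 + pre).

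| Pre-test angle, neutral = 0 | Change (degrees) | Percentage change | Percentage change, zero moved 90 degrees |
|---|---|---|---|
| −5 | +3 | −60% | +3.5% |
| −1 | +3 | −300% | +3.4% |
| +1 | +3 | +300% | +3.3% |
| +5 | +3 | +60% | +3.2% |
| +10 | +3 | +30% | +3.0% |

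This step needs no assumption about the participants. The percentage is set largely by the convention and the starting value.

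**3. How many pre-test peaks could be below neutral.** The documents do not say. Assuming a normal baseline with SD 4 to 6 degrees, the share below zero is 50% at a mean of 0 degrees, 31–37% at 2, 11–20% at 5 and 1–5% at 10. Out of 24 participants that is about 12, 7 to 9, 2 to 5, and 0 to 1.

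**4. Effect on the H4 test.** With two strategies, a repeated measures ANOVA is a paired t-test. Assumed inputs: n = 24; baseline SD 5 degrees; session noise SD 1; mean within-session gains of 5 and 2 degrees (true difference 3), each with SD 3; neutral as zero; signed denominator.

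For absolute change, the SD of the paired difference is √(3² + 3²) = 4.24 and the standardised effect is 3/4.24 = 0.71, which gives about 91% power at any baseline. Simulated results for percentage change:

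| Mean pre-test peak (degrees) | Power in the right direction | Worse strategy ranked first |
|---|---|---|
| 0 | about 1% | about 51% |
| 5 | 6% | 37% |
| 10 | 38% | 17% |
| 15 | 77% | 3% |
| 20 | 89% | 0.1% |

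With baseline SD 3, power is 80% at a mean of 10 and about 86–88% at a mean of 12, and the wrong ranking falls to 1.5% and 0.3%.

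**5. Two variations.** Dividing by the absolute pre-test value restores each participant's sign but not stability: power is about 20–35% at means of 0 to 8 degrees. With a smaller assumed effect (true difference 2 degrees, SD of change 2.5), absolute change has about 74–76% power, while signed percentage change has 0.8%, 5.5%, 31% and 62% at means of 0, 5, 10 and 15.

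**The case against.** The strongest objection is that the harm depends on inputs the documents do not contain. That stands. At a mean pre-test peak of 20 degrees, or at 10 to 12 degrees with little spread, percentage change costs only a few to about ten points of power. Four stronger readings should be resisted.

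- A reader might infer that the plan will score real improvements as worsening. That requires a zero at neutral with dorsiflexion positive, a signed denominator, a swing-phase peak and some pre-test peaks below neutral. None is stated. The neutral position in Section 5 is a target for setting stimulation in a seated subject, not the zero of the gait-analysis angle. Section 7 also speaks of walking rather than swing, and a peak over the whole stride cannot be lower than the swing peak.
- A reader might infer that the trial selects people with poor ankle flexion. The inclusion criteria in Section 6 contain no ankle-angle or foot-drop criterion, and Section 3 names hip, knee and/or ankle, so not every participant need have the deficit.
- A reader might extend the point to propulsive force and TMS responses. Nothing in the documents shows near-zero propulsion or absent responses at pre-test, or that such participants would be dropped.
- A reader might conclude that percentage change should be dropped altogether. For outcomes with a true zero, that is a preference rather than a correction.

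What the objection does not remove is the defect itself: the plan expressly applies a percentage to angles, and the result depends on a reference it does not state.

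**Conclusion.** The concern holds in a limited form. As written, Section 7 applies percentage change to peak knee and ankle flexion, for which that scale has no fixed meaning. This follows from the text and from step 2 alone. How much it costs rests on assumed baselines: in the model above, power falls from about 91% to anywhere between 1% and 89%, and the worse strategy is ranked first in anything from about half of trials to almost none. Reversal of individual improvements is a possibility under the four stated conditions, not an established result.

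The point should be fixed but is not critical. The study is powered on paretic propulsive force, ankle flexion is one of several H4 outcomes, and the Section 7 tests of H1 and H3 do not specify percentage change.

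**What to change.** In Section 7, for H4:

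- Analyse peak knee and peak ankle flexion as within-session change in degrees rather than percent.
- State the zero and sign convention for each angle.
- State the gait phase from which the peak is taken, so that Section 7 (walking) agrees with the FastFES part of Section 3 (swing).
- Write out the percentage formula for the outcomes that keep it. Those with a true zero, such as speed, endurance and propulsive force, may do so.

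The cost is a sentence or two, with no new data or visits. The small downside is that joint-angle effects will no longer share a percentage scale with the other outcomes; standardised mean changes can be shown beside them if a common scale is wanted.
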